5. STUDY POPULATION

Screening for eligible participants will be performed within 8 weeks before administration of the study intervention. Refer to Section 5.4, Screen Failures for conditions under which the repeat of any screening procedures are allowed.

The inclusion and exclusion criteria for enrolling participants in this study are described below. If there is a question about these criteria, the investigator must consult with the appropriate sponsor representative and resolve any issues before enrolling a participant in the study. Waivers are not allowed.

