5.2. Exclusion Criteria

Any potential participant who meets any of the following criteria will be excluded from participating in the study:

1. Has severe extensive colitis as evidenced by:
 - a. Current hospitalization for the treatment of UC.

OR

 - b. Investigator judgment that the participant is likely to require a colectomy within 12 weeks of baseline.

OR

 - c. Symptom complex at screening or baseline visits that includes at least 4 of the following:
 - 1) Diarrhea with ≥ 6 bowel movements/day with macroscopic blood in stool
 - 2) Focal severe or rebound abdominal tenderness
 - 3) Persistent fever ($\geq 37.5^{\circ}\text{C}$)
 - 4) Tachycardia (>100 beats/minute)
 - 5) Anemia (hemoglobin <8.5 g/dL)
2. Has UC limited to the rectum only or to <20 cm of the colon.
3. Presence of a stoma.
4. Presence or history of a fistula.
5. Require, or required within the 2 months before screening, surgery for active gastrointestinal bleeding, peritonitis, intestinal obstruction, or intra-abdominal or pancreatic abscess requiring surgical drainage, or other conditions possibly confounding the evaluation of benefit from study intervention treatment.

6. Presence of symptomatic colonic or small bowel obstruction, confirmed by objective radiographic or endoscopic evidence of a stricture with resulting obstruction (dilation of the colon or small bowel proximal to the stricture on barium radiograph or an inability to traverse the stricture at endoscopy).
7. History of extensive colonic resection (eg, less than 30 cm of colon remaining) that would prevent adequate evaluation of the effect of study intervention on clinical disease activity.
8. History of colonic mucosal dysplasia. Participants will not be excluded from the study because of a pathology finding of “indefinite for dysplasia with reactive atypia.”
9. Presence on screening endoscopy of adenomatous colonic polyps, if not removed before study entry, or history of adenomatous colonic polyps that were not removed.
10. Diagnosis of indeterminate colitis, microscopic colitis, ischemic colitis, or Crohn’s disease or clinical findings suggestive of Crohn’s disease.
11. Criterion modified per Amendment 2.
 - 11.1. Has a stool culture or other examination positive for an enteric pathogen, including *Clostridium difficile* toxin, within 4 months before the first administration of study intervention, unless a repeat examination is negative and there are no signs of ongoing infection with that pathogen.

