Concomitant or previous medical therapies received

12. Has received the following prescribed medications or therapies:
 - a. A biologic therapy targeted at IL-12 and/or IL-23 (eg, ustekinumab, briakinumab, guselkumab, mirikizumab, tildrakizumab, brazikumab, or risankizumab).
 - b. A biologic therapy targeted at TNF (eg, golimumab, infliximab, etanercept, adalimumab, or certolizumab pegol).
 - c. Natalizumab within 12 months of first study intervention administration.
 - d. Agents that deplete B or T cells (eg, rituximab, alemtuzumab) within 12 months of first study intervention administration, or continue to manifest depletion of B or T cells more than 12 months after completion of therapy with lymphocyte-depleting agents.
 - e. Any investigational drug within 4 weeks before first administration of study intervention or within 5 half-lives of the investigational agent, whichever is longer.
 - f. Apheresis (eg, Adacolumn or Cellsorba apheresis) within 2 weeks before the first administration of study intervention.

Infections or predisposition to infections

13. Has a history of latent or active granulomatous infection, including histoplasmosis or coccidioidomycosis, before screening. Refer to Inclusion Criterion 11 for information regarding eligibility with a history of latent TB.
14. Has a history of, or ongoing, chronic or recurrent infectious disease, including but not limited to, chronic renal infection, chronic chest infection (eg, bronchiectasis), sinusitis, recurrent urinary tract infection (eg, recurrent pyelonephritis, recurrent cystitis), an open, draining, or infected skin wound, or an ulcer.
15. Has a chest radiograph within 3 months before the first administration of study intervention that shows an abnormality suggestive of a malignancy or current active infection, including TB.
16. Has a history of being human immunodeficiency virus (HIV) antibody-positive, or tests positive for HIV at screening.
17. Is seropositive for antibodies to hepatitis C virus (HCV) without a history of successful treatment, defined as being negative for HCV ribonucleic acid (RNA) at least 24 weeks after completing antiviral treatment.
18. Tests positive for hepatitis B virus (HBV) infection (see Appendix 5 [Section 10.5], Hepatitis B Virus Screening with HBV DNA Testing).

Note: For participants who are not eligible for this study due to HIV, HCV, and HBV test results, consultation with a physician with expertise in the treatment of those infections is recommended.

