
19. Has had a Bacille Calmette-Guérin (BCG) vaccination within 12 months or any other live bacterial or live viral vaccination within 12 weeks before baseline.
20. Has or has had a nontuberculous mycobacterial infection or clinically significant opportunistic infection (eg, cytomegalovirus colitis, pneumocystosis, invasive aspergillosis).
21. Has had a clinically significant infection (eg, hepatitis, sepsis, pneumonia, pyelonephritis), has been hospitalized for an infection, or has been treated with parenteral antibiotics for an infection within 2 months before first administration of study intervention. Treated and resolved infections not considered clinically significant at the discretion of the investigator need not be exclusionary (eg, acute upper respiratory tract infection, uncomplicated urinary tract infection).
22. Has current signs or symptoms of a clinically significant infection. Ongoing infections not considered clinically significant at the discretion of the investigator need not be exclusionary (eg, acute upper respiratory tract infection, uncomplicated urinary tract

infection).

23. Has evidence of a herpes zoster infection ≤ 8 weeks before baseline.

Malignancy or increased potential for malignancy

24. Has any known malignancy or has a history of malignancy (with the exception of basal cell carcinoma; squamous cell carcinoma in situ of the skin; or cervical carcinoma in situ that has been treated with no evidence of recurrence; or squamous cell carcinoma of the skin that has been treated with no evidence of recurrence within 5 years before screening).
25. Presence or history of lymphoproliferative disease including lymphoma, or signs and symptoms suggestive of possible lymphoproliferative disease, such as lymphadenopathy of unusual size or location (eg, nodes in the posterior triangle of the neck, infraclavicular, epitrochlear, or periaortic areas), or clinically significant hepatomegaly or splenomegaly, or monoclonal gammopathy of undetermined significance.

Coexisting medical conditions or past medical history

26. Has known allergies, hypersensitivity, or intolerance to guselkumab or golimumab or their excipients (refer to the respective guselkumab and golimumab IBs).
27. Has severe, progressive, or uncontrolled renal, hepatic, hematologic, endocrine, pulmonary, cardiac, neurologic, psychiatric, or cerebral disease, or signs or symptoms thereof.

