8. STUDY ASSESSMENTS AND PROCEDURES

Overview

The SoA (Section 1.3) summarizes the frequency and timing of efficacy, PK, immunogenicity, biomarker (PD), pharmacogenomic, medical resource utilization, and safety measurements applicable to this study.

All visit-specific PRO assessments should be conducted/completed before any tests, procedures, or other consultations to prevent influencing participant perceptions.

Blood collections for PK and PD assessments should be kept as close to the specified time as possible. Other measurements may be done earlier than specified time points if needed. Actual dates and times of assessments will be recorded in the source documentation.

For women of childbearing potential only, additional serum or urine pregnancy tests may be performed, as determined necessary by the investigator or required by local regulation, to establish the absence of pregnancy at any time during the participation in the study.

Medical resource utilization data will be collected. Refer to Section 8.9, Medical Resource Utilization for details.

At their last study visit, each study participant will be invited to complete an IEC/IRB approved Experience Survey, to share his/her experience as a volunteer in this study. The responses will be collected by an external party and provided anonymously to the sponsor.

Screening Phase

After written informed consent has been obtained and within 8 weeks before randomization, all screening evaluations (eg, laboratory test results, clinical data, and concomitant medication data) that establish participant eligibility will be performed by the principal investigator or designee to confirm that the participant satisfies all inclusion criteria and does not violate any exclusion criteria. Participants who meet all of the inclusion and none of the exclusion criteria can be enrolled in the study. Every effort should be made to adhere to the SoA (Section 1.3) for each participant. The collection of AEs will start at the time informed consent is obtained.

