10.5. Appendix 5: Hepatitis B Virus (HBV) Screening with HBV DNA Testing

Participants must undergo screening for hepatitis B virus (HBV). At a minimum, this includes testing for HBsAg (HBV surface antigen), anti-HBs (HBV surface antibody), and anti-HBc total (HBV core antibody total):

- Participants who test negative for all HBV screening tests (ie, HBsAg-, anti-HBc-, and anti-HBs-) **are eligible** for this protocol.
- Participants who test **negative** for surface antigen (HBsAg-) and test **positive** for core antibody (anti-HBc+) **and** surface antibody (anti-HBs+) **are eligible** for this protocol.
- Participants who test **positive only** for **surface antibody** (anti-HBs+) **are eligible** for this protocol.
- Participants who test **positive** for surface antigen (HBsAg+) **are NOT eligible** for this protocol, regardless of the results of other hepatitis B tests.
- Participants who test **positive only** for **core antibody** (anti-HBc+) must undergo further testing for the presence of hepatitis B virus deoxyribonucleic acid (HBV DNA) test. If the HBV DNA test is **negative**, the participant **is eligible** for this protocol. If the HBV DNA test is **positive**, the participant **is NOT eligible** for this protocol. In the event the HBV DNA test cannot be performed, the participant **is NOT eligible** for this protocol.

These eligibility criteria based on HBV test results are also represented in Table 1 below.

Table 1: Eligibility based on hepatitis B virus test results			
HEPATITIS B TEST RESULT			STATUS
Hepatitis B surface antigen (HBsAg)	Hepatitis B surface antibody (anti-HBs)	Hepatitis B core antibody (anti-HBc total)	
negative	negative	negative	Eligible
negative	(+)	negative	
negative	(+)	(+)	
(+)	negative or (+)	negative or (+)	Not eligible
negative	negative	(+)	(Require testing for presence of HBV DNA*)

* If HBV DNA is detectable, the participant is not eligible for this protocol. If HBV DNA testing cannot be performed, or there is evidence of chronic liver disease, the participant is not eligible for the protocol.

For participants who **are not eligible for this protocol due to HBV test results**, consultation with a physician with expertise in the treatment of HBV infection is recommended.

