4.5. Protocol Deviations

Participants with a major protocol deviation will be summarized by treatment group based on the FAS (Section 2.2.2). Major protocol deviations will be categorized as study intervention administration deviations, study entry criteria not met, prohibited concomitant medications deviations, withdrawal criteria met but not withdrawn, or other (including a sub-category for COVID-19 related deviations).

In addition, participants who did not meet study entry criteria will be further summarized by category (UC disease criteria, Medication criteria, Laboratory criteria, Medical history criteria, and other) based on the FAS. Further, participants who had study intervention administration

deviations will be further summarized by category identified prior to unblinding (e.g., received wrong study intervention administration, missed study intervention administration, received study intervention administration outside of protocol specified window).

A listing of participants who had a major protocol deviation (including COVID-19 related deviations), a more detailed listing of participants who did not meet study entry criteria (by category), and a more detailed listing of participants who had a study intervention administration deviations will be provided. A listing of participants with minor protocol deviations related to COVID-19 will also be provided.

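### In Protocol Appendix 5, the bullet for participants positive only for hepatitis B core antibody omits the chronic liver disease bar that the table footnote sets for the same participants

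*Protocol*

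**What the plan says.** Exclusion criterion 18 in Protocol Section 5.2 brings the appendix into the eligibility rules: "Tests positive for hepatitis B virus (HBV) infection (see Appendix 5 [Section 10.5], Hepatitis B Virus Screening with HBV DNA Testing". Appendix 5 then sets out five bullets by serology pattern and follows them with a table that it describes as presenting the same criteria.

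The fifth bullet covers participants positive only for anti-HBc, who must have an HBV DNA test. It makes them ineligible if the test is positive or cannot be done. For the remaining outcome it says: "If the HBV DNA test is negative, the participant is eligible for this protocol".

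The table row for the same pattern (surface antigen negative, surface antibody negative, core antibody positive) calls for DNA testing and carries an asterisk. The footnote bars a participant with detectable DNA and continues: "If HBV DNA testing cannot be performed, or there is evidence of chronic liver disease, the participant is not eligible for the protocol".

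**The concern.** The last condition in the footnote, evidence of chronic liver disease, appears in none of the five bullets. A site that works from the bullet could therefore enrol a participant whom the footnote bars.

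This is a safety entry rule in a trial that combines two immunomodulatory biologics. HBV testing appears in the Schedule of Activities (Section 1.3) only at screening, so the entry rule is the trial's scheduled hepatitis B check. The liver algorithm in Appendix 7 is written for subjects without underlying liver disease. For those with pre-existing disease it only encourages consultation with the hepatic safety group.

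There is also a reporting consequence. Section 5 of the protocol does not allow waivers, so such an enrolment would count as an entry-criteria deviation. Under SAP Section 4.5, "participants who did not meet study entry criteria will be further summarized by category". A site could be recorded as deviating after following a sentence that called the participant eligible.

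**Working it through.** No figure in the plan depends on this point, so the check compares the two texts and then looks for another rule that removes the difference.

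**Step 1. Bars on the isolated anti-HBc pattern**

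- Footnote: (1) HBV DNA detectable; (2) DNA test cannot be performed; (3) evidence of chronic liver disease. Total 3.
- Bullet: (1) and (2) only. Total 2.
- Missing from the bullet: 3 − 2 = 1.
- Bullets affected: 1 of 5.

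**Step 2. The possible cases**

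| Case (anti-HBc only) | Bullet | Footnote | Agree? |
|---|---|---|---|
| DNA positive | not eligible | not eligible | yes |
| DNA test not possible | not eligible | not eligible | yes |
| DNA negative, no evidence of chronic liver disease | eligible | no bar | yes |
| DNA negative, evidence of chronic liver disease | eligible | not eligible | **no** |

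One of four cases differs.

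**Step 3. Does another criterion settle that case?**

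- Exclusion 18 refers to the appendix as a whole and does not choose between bullet and footnote.
- Exclusion 27 reads: "Has severe, progressive, or uncontrolled renal, hepatic, hematologic, endocrine, pulmonary, cardiac, neurologic, psychiatric, or cerebral disease, or signs or symptoms thereof". This is narrower than any evidence of chronic liver disease; stable, non-severe disease is not clearly caught.
- Inclusion 10f requires ALT and AST within 2 x ULN. Chronic liver disease can be present below that limit.
- Exclusion 37 leaves the matter to the investigator's opinion and so does not guarantee exclusion.

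A participant who is anti-HBc positive only and DNA negative, with stable, non-severe chronic liver disease and ALT/AST within 2 x ULN, can pass all of these. The footnote still bars that person.

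**Step 4. Which text governs?**

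The lead-in to Section 5.2 says: "Any potential participant who meets any of the following criteria will be excluded from participating in the study". Section 8 says: "Participants who meet all of the inclusion and none of the exclusion criteria can be enrolled in the study". Entry is therefore decided by whether any bar applies, which favours the footnote. The protocol does not say this directly for Appendix 5; it has to be inferred.

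**Step 5. Reach into the analysis**

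The Full Analysis Set (SAP Section 2.2.2) contains every randomized participant who receives at least one dose and does not remove anyone for an entry deviation. The primary comparison, its test level and the sample size in Protocol Section 9.2 do not use the hepatitis rule.

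**The case against.** The strongest reply is that the two texts do not truly oppose each other. The bullets and table concern eligibility as determined by hepatitis B test results, and chronic liver disease is not such a result. In every Appendix 5 bullet, eligible can only mean eligible as far as HBV is concerned: even a participant negative on all three tests must still meet every other criterion. The bullet does not say that a negative DNA result overrides other findings. A site that applies the stricter footnote satisfies both texts, and the footnote sits in the same short appendix on the row for this serology.

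Most of this stands. A reader might infer that Appendix 5 contradicts itself, or that it waves DNA-negative participants through whatever else is known about them. The documents do not support that; the bullet is incomplete and does not set up a rival rule. Nor do they support reading the footnote as a general bar on chronic liver disease, because it attaches to this one serology row.

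What does not stand is the suggestion that the omission is harmless drafting. The footnote's condition is part of the HBV rule for that row, so reading eligible as HBV-only does not remove the difference. The table is introduced as a restatement, which gives a site little reason to expect an extra bar there.

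The safeguards are real but partial. Section 5 says: "If there is a question about these criteria, the investigator must consult with the appropriate sponsor representative". That helps only a site that notices there is a question. Section 8.2.5 calls for suspension of dosing when ALT or AST exceeds 3 x ULN together with bilirubin above 2 x ULN, which acts after enrolment.

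**Conclusion.** The point holds as an omission. For participants positive only for anti-HBc, the bullet leaves out one of the three bars in the footnote, and the texts diverge in one of four cases. The footnote is best read as governing. Other criteria catch many, but not all, of the people in that case.

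The size in participants cannot be given. The documents state neither the number screened nor the frequency of isolated anti-HBc positivity or of chronic liver disease in this population, and the number may be zero. The counts above describe the text and do not measure risk.

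The conclusion assumes that the footnote states the sponsor's intention. If the sponsor meant the bullet to be complete, the texts would still need aligning, in the other direction. No change to power, alpha, the estimand or any analysis should be inferred. This is a minor patient-safety consistency correction.

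**What to change.** In the fifth bullet of Appendix 5, insert *and there is no evidence of chronic liver disease* after the statement that the DNA test is negative, so that eligibility depends on both conditions. The bullet then carries the same three bars as the footnote.

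The cost is one clause in the next amendment. It needs no new test and produces no screen failures beyond those the footnote already requires. The appendix does not say what counts as evidence of chronic liver disease, so a short definition in the same amendment would help sites apply the rule alike. That is a useful addition, and the correction does not depend on it.

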10.6. Appendix 6: Regulatory, Ethical, and Study Oversight Considerations

REGULATORY AND ETHICAL CONSIDERATIONS

Investigator Responsibilities

The investigator is responsible for ensuring that the study is performed in accordance with the protocol, current ICH guidelines on Good Clinical Practice (GCP), the latest version of the Declaration of Helsinki, and applicable regulatory and country-specific requirements.

Good Clinical Practice is an international ethical and scientific quality standard for designing, conducting, recording, and reporting studies that involve the participation of human participants. Compliance with this standard provides public assurance that the rights, safety, and well-being of study participants are protected, consistent with the principles that originated in the Declaration of Helsinki, and that the study data are credible.

Protocol Amendments

Neither the investigator nor the sponsor will modify this protocol without a formal amendment by the sponsor. All protocol amendments must be issued by the sponsor, and signed and dated by the investigator. Protocol amendments must not be implemented without prior IEC/IRB approval, or when the relevant competent authority has raised any grounds for non-acceptance, except when necessary to eliminate immediate hazards to the participants, in which case the amendment must be promptly submitted to the IEC/IRB and relevant competent authority. Documentation of amendment approval by the investigator and IEC/IRB must be provided to the sponsor. When the change(s) involve only logistic or administrative aspects of the study, the IEC/IRB (where required) only needs to be notified.

During the course of the study, in situations where a departure from the protocol is unavoidable, the investigator or other physician in attendance will contact the appropriate sponsor representative listed in the Contact Information page(s), which will be provided as a separate document. Except in emergency situations, this contact should be made before implementing any departure from the protocol. In all cases, contact with the sponsor must be made as soon as possible to discuss the situation and agree on an appropriate course of action. The data recorded in the Data Collection System (DCS) and source documents will reflect any departure from the protocol, and the source documents will describe this departure and the circumstances requiring it.

Regulatory Approval/Notification

This protocol and any amendment(s) must be submitted to the appropriate regulatory authorities in each respective country, if applicable. A study may not be initiated until all local regulatory requirements are met.

Required Prestudy Documentation

The following documents must be provided to the sponsor before shipment of study intervention to the study site:

- Protocol and amendment(s), if any, signed and dated by the principal investigator
- A copy of the dated and signed (or sealed, where appropriate per local regulations), written IEC/IRB approval of the protocol, amendments, ICF, any recruiting materials, and if applicable, participant compensation programs. This approval must clearly identify the specific protocol by title and number and must be signed (or sealed, where appropriate per local regulations) by the chairman or authorized designee.
- Name and address of the IEC/IRB, including a current list of the IEC/IRB members and their function, with a statement that it is organized and operates according to GCP and the applicable laws and regulations. If accompanied by a letter of explanation, or equivalent, from the IEC/IRB, a general statement may be substituted for this list. If an investigator or a member of the study-site personnel is a member of the IEC/IRB, documentation must be obtained to state that this person did not participate in the deliberations or in the vote/opinion of the study.
- Regulatory authority approval or notification, if applicable
- Signed and dated statement of investigator (eg, Form Food and Drug Administration [FDA] 1572), if applicable
- Documentation of investigator qualifications (eg, curriculum vitae)
- Completed investigator financial disclosure form from the principal investigator, where required
- Signed and dated clinical trial agreement, which includes the financial agreement
- Any other documentation required by local regulations

The following documents must be provided to the sponsor before enrollment of the first participant:

- Completed investigator financial disclosure forms from all subinvestigators
- Documentation of subinvestigator qualifications (eg, curriculum vitae)
- Name and address of any local laboratory conducting tests for the study, and a dated copy of current laboratory normal ranges for these tests, if applicable
- Local laboratory documentation demonstrating competence and test reliability (eg, accreditation/license), if applicable

Independent Ethics Committee or Institutional Review Board

Before the start of the study, the investigator (or sponsor where required) will provide the IEC/IRB with current and complete copies of the following documents (as required by local regulations):

- Final protocol and, if applicable, amendments
- Sponsor-approved ICF (and any other written materials to be provided to the participants)
- Investigator's Brochure (or equivalent information) and amendments/addenda
- Sponsor-approved participant recruiting materials

- Information on compensation for study-related injuries or payment to participants for participation in the study, if applicable
- Investigator's curriculum vitae or equivalent information (unless not required, as documented by the IEC/IRB)
- Information regarding funding, name of the sponsor, institutional affiliations, other potential conflicts of interest, and incentives for participants
- Any other documents that the IEC/IRB requests to fulfill its obligation

This study will be undertaken only after the IEC/IRB has given full approval of the final protocol, amendments (if any, excluding the ones that are purely administrative, with no consequences for participants, data or study conduct, unless required locally), the ICF, applicable recruiting materials, and participant compensation programs, and the sponsor has received a copy of this approval. This approval letter must be dated and must clearly identify the IEC/IRB and the documents being approved.

Approval for the collection of optional samples for research and for the corresponding ICF must be obtained from the IEC/IRB. Approval for the protocol can be obtained independent of this optional research component.

During the study the investigator (or sponsor where required) will send the following documents and updates to the IEC/IRB for their review and approval, where appropriate:

- Protocol amendments (excluding the ones that are purely administrative, with no consequences for participants, data or study conduct)
- Revision(s) to ICF and any other written materials to be provided to participants
- If applicable, new or revised participant recruiting materials approved by the sponsor
- Revisions to compensation for study-related injuries or payment to participants for participation in the study, if applicable
- New edition(s) of the IB and amendments/addenda
- Summaries of the status of the study at intervals stipulated in guidelines of the IEC/IRB (at least annually)
- Reports of adverse events that are serious, unlisted/unexpected, and associated with the study intervention
- New information that may adversely affect the safety of the participants or the conduct of the study
- Deviations from or changes to the protocol to eliminate immediate hazards to the participants
- Report of deaths of participants under the investigator's care
- Notification if a new investigator is responsible for the study at the site

- Development Safety Update Report and Line Listings, where applicable
- Any other requirements of the IEC/IRB

For all protocol amendments (excluding the ones that are purely administrative, with no consequences for participants, data or study conduct), the amendment and applicable ICF revisions must be submitted promptly to the IEC/IRB for review and approval before implementation of the change(s).

At least once a year, the IEC/IRB will be asked to review and reapprove this study, where required.

At the end of the study, the investigator (or sponsor where required) will notify the IEC/IRB about the study completion (if applicable, the notification will be submitted through the head of investigational institution).

Country Selection

This study will only be conducted in those countries where the intent is to launch or otherwise help ensure access to the developed product if the need for the product persists, unless explicitly addressed as a specific ethical consideration in Section 4.2.5, Study-Specific Ethical Design Considerations.

Other Ethical Considerations

For study-specific ethical design considerations, refer to Section 4.2.5.

FINANCIAL DISCLOSURE

Investigators and subinvestigators will provide the sponsor with sufficient, accurate financial information in accordance with local regulations to allow the sponsor to submit complete and accurate financial certification or disclosure statements to the appropriate regulatory authorities. Investigators are responsible for providing information on financial interests during the course of the study and for 1 year after completion of the study.

Refer to Required Prestudy Documentation (above) for details on financial disclosure.

INFORMED CONSENT PROCESS

Each participant must give written consent according to local requirements after the nature of the study has been fully explained. The ICF(s) must be signed before performance of any study-related activity. The ICF(s) that is/are used must be approved by both the sponsor and by the reviewing IEC/IRB and be in a language that the participant can read and understand. The informed consent should be in accordance with principles that originated in the Declaration of Helsinki, current ICH and GCP guidelines, applicable regulatory requirements, and sponsor policy.

Before enrollment in the study, the investigator or an authorized member of the study-site personnel must explain to potential participants the aims, methods, reasonably anticipated benefits, and potential hazards of the study, and any discomfort participation in the study may

entail. Participants will be informed that their participation is voluntary and that they may withdraw consent to participate at any time. They will be informed that choosing not to participate will not affect the care the participant will receive. Finally, they will be told that the investigator will maintain a participant identification register for the purposes of long-term follow up if needed and that their records may be accessed by health authorities and authorized sponsor personnel without violating the confidentiality of the participant, to the extent permitted by the applicable law(s) or regulations. By signing the ICF the participant is authorizing such access. It also denotes that the participant agrees to allow his or her study physician to recontact the participant for the purpose of obtaining consent for additional safety evaluations, and subsequent disease-related treatments, if needed.

The participant will be given sufficient time to read the ICF and the opportunity to ask questions. After this explanation and before entry into the study, consent should be appropriately recorded by means of the participant's personally dated signature. After having obtained the consent, a copy of the ICF must be given to the participant.

A participant may be rescreened 1 time. Participants who are rescreened are required to sign a new ICF.

Completion of screening and randomization procedures within the specified screening window of approximately 8 weeks is required. If any delay leads to the expiration of time-specific assessments (eg, TB, chest radiograph, endoscopy), the participant will be considered a screen failure because he/she will not meet eligibility criteria, and the expired assessments (along with the non-time-specific laboratory tests) will have to be repeated on rescreening.

Participants will be asked for consent to provide optional samples for research (where local regulations permit). After informed consent for the study is appropriately obtained, the participant will be asked to sign and personally date a separate ICF indicating agreement to participate in the optional research component. Refusal to participate in the optional research will not result in ineligibility for the study. A copy of this signed ICF will be given to the participant.

DATA PROTECTION

Privacy of Personal Data

The collection and processing of personal data from participants enrolled in this study will be limited to those data that are necessary to fulfill the objectives of the study.

These data must be collected and processed with adequate precautions to ensure confidentiality and compliance with applicable data privacy protection laws and regulations. Appropriate technical and organizational measures to protect the personal data against unauthorized disclosures or access, accidental or unlawful destruction, or accidental loss or alteration must be put in place. Sponsor personnel whose responsibilities require access to personal data agree to keep the identity of participants confidential.

The informed consent obtained from the participant includes explicit consent for the processing of personal data and for the investigator/institution to allow direct access to his or her original medical records (source data/documents) for study-related monitoring, audit, IEC/IRB review, and regulatory inspection. This consent also addresses the transfer of the data to other entities and to other countries.

The participant has the right to request through the investigator access to his or her personal data and the right to request rectification of any data that are not correct or complete. Reasonable steps will be taken to respond to such a request, taking into consideration the nature of the request, the conditions of the study, and the applicable laws and regulations.

Exploratory DNA, biomarker, PK, and immunogenicity research is not conducted under standards appropriate for the return of data to participants. In addition, the sponsor cannot make decisions as to the significance of any findings resulting from exploratory research. Therefore, exploratory research data will not be returned to participants or investigators, unless required by law or local regulations. Privacy and confidentiality of data generated in the future on stored samples will be protected by the same standards applicable to all other clinical data.

LONG-TERM RETENTION OF SAMPLES FOR ADDITIONAL FUTURE RESEARCH

Samples collected in this study may be stored for up to 15 years (or according to local regulations) for additional research. The start of the storage period is defined as last participant last visit. Samples will only be used to understand guselkumab and golimumab, to understand UC, to understand differential intervention responders, and to develop tests/assays related to guselkumab and golimumab and UC. The research may begin at any time during the study or the post-study storage period.

Stored samples will be coded throughout the sample storage and analysis process and will not be labeled with personal identifiers. Participants may withdraw their consent for their samples to be stored for research (refer to Section 7.2.1, Withdrawal From the Use of Research Samples).

COMMITTEES STRUCTURE

Data Monitoring Committee

Details regarding the DMC are presented in Section 9.5.1.

PUBLICATION POLICY/DISSEMINATION OF CLINICAL STUDY DATA

All information, including but not limited to information regarding guselkumab and golimumab or the sponsor's operations (eg, patent application, formulas, manufacturing processes, basic scientific data, prior clinical data, formulation information) supplied by the sponsor to the investigator and not previously published, and any data, including pharmacogenomic or exploratory biomarker research data, generated as a result of this study, are considered confidential and remain the sole property of the sponsor. The investigator agrees to maintain this information in confidence and use this information only to accomplish this study, and will not use it for other purposes without the sponsor's prior written consent.

The investigator understands that the information developed in the study will be used by the sponsor in connection with the continued development of guselkumab and golimumab, and thus may be disclosed as required to other clinical investigators or regulatory agencies. To permit the information derived from the clinical studies to be used, the investigator is obligated to provide the sponsor with all data obtained in the study.

The results of the study will be reported in a Clinical Study Report generated by the sponsor and will contain data from all study sites that participated in the study as per protocol. Recruitment performance or specific expertise related to the nature and the key assessment parameters of the study will be used to determine a coordinating investigator for the study. Results of pharmacogenomic or exploratory biomarker analyses performed after the Clinical Study Report has been issued will be reported in a separate report and will not require a revision of the Clinical Study Report.

Study participant identifiers will not be used in publication of results. Any work created in connection with performance of the study and contained in the data that can benefit from copyright protection (except any publication by the investigator as provided for below) shall be the property of the sponsor as author and owner of copyright in such work.

